#### 7.3.3 Duration/Study Day/Time

Study day will be calculated as the number of days from first dose of SP-102 TF or placebo injection.

- date of event – date of first dose of SP-102 TF or placebo + 1, for events on or after first dose
- date of event – date of first dose of SP-102 TF or placebo, for events before first dose.

For all time to event analyses, subjects not reporting the specified endpoint will be censored at the time that the subjects were last known not to have experienced the endpoint. The last visit is a censoring event, and events that occur after the last visit will be disregarded in the statistical analysis. For all endpoints not encompassing death, all deaths will be treated as censoring events. In complex cases where the censoring time of the subject is uncertain, the case will be reviewed

by the Worldwide Clinical Trials (WCT) statistician and a censoring time will be assigned before database lock.

### 7.3.4 Conventions for Missing and Partial Dates

All rules explained below for partial/missing dates will be followed unless contradicted by any other data recorded on the electronic Case Report Form (eCRF).

All dates presented in the individual subject listings will be as recorded on the eCRF (i.e., not completed as per the below rules).

### 7.3.5 Missing/Partial Start/Stop Date of Adverse Events and Concomitant Medications

Missing and partial start and stop date will be imputed for analysis purposes as follows:

Partial or missing stop date will be imputed as follows:

- If the stop date is completely missing and the event has resolved or the subject has stopped taking the concomitant medication, the stop date will be imputed as the date of the subject's last clinic visit in the study.
- If only the year is known, the stop date will be imputed as "31-Dec" of that year or as the date of the subject's last clinic visit in the study if in the same year.
- If the month and year are known, the stop date will be imputed as the last day of that month unless the stop date corresponds to the same month as the subject's last clinic visit in which case the date of subject's last clinic visit in the study will be used instead.

Missing start date will be imputed as follows:

- If the stop date occurs on or after the index injection or the event/concomitant medication is ongoing, the start date will be imputed as the date of the index injection.
- If the stop date occurs before the index injection, the start date of the event/concomitant medication will be imputed as the subject's screening date or the stop date of the event/concomitant medication whichever the earlier.

Partial start date (year present, but month and day missing)

- If the stop date occurs on or after the index injection or the event/concomitant medication is ongoing, and the year is the same as the year of index injection the start date will be imputed as the date of the index injection. If the year is different from the year of index injection "01-Jan" will be used.

- If the stop date occurs before the index injection, the start date of the event/concomitant medication will be imputed as the “01-Jan” of the same year.

#### Partial start date (month and year present, but day missing)

- If the stop date occurs on or after the index injection or the event/concomitant medication is ongoing, the start date will be imputed as the first day of the same month and year unless this partial start date is in same month as the index injection in which case the date of index injection will be used.
- If the stop date occurs before the index injection, the start date will be imputed as the first day of the month and year of the partial stop date.

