#### 7.13.1 Adverse Events

Adverse events will be recorded using MedDRA v23.1 or a more up-to-date version by the time of database lock. A treatment emergent adverse event (TEAE) is defined as:

- Any AE that has an onset on or after the first dose of SP-102 or placebo
- Any pre-existing AE that has worsened in severity on or after the first dose of SP-102 or placebo.

A treatment-related TEAE is any study medication related TEAE and/or study procedure related TEAE.

A study medication treatment-related AE is defined as one of the following; possibly related, probably related, or definitely related to the study drug. If an AE has a missing relationship to study medication it is assumed to be related to the study drug for analysis purposes.

A study procedure treatment-related AE is defined as an AE related to the study procedure.

The intensity/standard toxicity grade of an AE is defined as an AE being Grade 1 (Mild), Grade 2 (Moderate), Grade 3 (Severe), or Grade 4 (Life-Threatening).

Severe intensity (Grade 3) will be assumed for an AE with missing intensity.

The summary of TEAEs will include the total number and percentage of subjects reporting an event. In counting the number of events reported, a continuous event, i.e. reported more than once and which did not cease, will be counted only once; non-continuous AEs reported several times by the same subject will be counted as multiple events.

TEAEs will be assigned to one of the two treatments (SP-102 or Placebo). AEs starting while on Placebo but before the repeat injection will be assigned to Placebo. AEs starting on or after the repeat injection of SP-102 will be assigned to SP-102. Any pre-existing TEAE that started during the Placebo use and that has worsened in severity on or after the repeat injection of SP-102 will be assigned to SP-102.

Any TEAEs will be summarized by treatment, for each post-randomization treatment period:

- Entire treatment period
- Occurring after the randomization injection, but prior to a second injection (of SP-102)
- Occurring after the second injection (of SP-102)

The following incidence (number and percent of subjects reporting the AE at least once during the study) of TEAEs tables will be presented:

- Overall incidence and the number of TEAEs, related TEAEs, serious adverse events (SAEs), related SAEs, TEAEs leading to withdrawal, and TEAEs leading to death.
- TEAE by system organ class and preferred term, incidence and number of events

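### AE start-date imputation in SAP 7.3.5 ignores the repeat injection, so doubtful onsets fall before it in the onset-based AE tables; separately, Exposed in the 12-week tables has no Week 12 limit

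*SAP*

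**What the plan says.** SAP 7.3.5 imputes incomplete start dates for AEs that stopped on or after the index injection or are ongoing:

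- Fully missing start: if "the event/concomitant medication is ongoing, the start date will be imputed as the date of the index injection".
- Year only: if "the year is the same as the year of index injection the start date will be imputed as the date of the index injection"; in any other year, 1 January.
- Month and year: the first of the month, "unless this partial start date is in same month as the index injection in which case the date of index injection will be used".

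None of these rules mentions the repeat injection. SAP 7.3.4 adds that the rules "will be followed unless contradicted by any other data recorded on the electronic Case Report Form".

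SAP 7.13.1 uses the resulting dates in three places: the assignment of each AE to Placebo or SP-102 ("AEs starting on or after the repeat injection of SP-102 will be assigned to SP-102"), the tables before and after the second injection, and the Placebo versus SP-102 table within PBO/SP-102 subjects. An AE that began on placebo moves to SP-102 only if it worsened on or after the repeat. The same section sets two other defaults for missing data: "If an AE has a missing relationship to study medication it is assumed to be related to the study drug for analysis purposes" and "Severe intensity (Grade 3) will be assumed for an AE with missing intensity".

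For tables through 12 weeks, SAP 7.9 and 7.13.1 define Exposed as SP-102 at index and/or a repeat injection, with no limit on when the repeat was given. Repeats are allowed from Week 4 to Week 20 (SAP 2), and the outputs are produced again for the full analysis (SAP 7.1).

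**The concern.** The tables turn on one date, the repeat injection, and the imputation rule is written around another. When an incomplete start could lie on either side of the repeat, the rule places it before, unless the repeat fell on the imputed day itself. The error therefore has one direction. In PBO/SP-102 subjects it takes AEs from SP-102 and gives them to Placebo. That is opposite to the SAP's defaults for missing relationship and missing intensity, both of which lean against the drug.

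Safety of single and repeat SP-102 injection is a secondary objective (SAP 3.2). The affected tables describe the repeat injection and report counts and percentages by preferred term, so for a rare term one event can matter.

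The secondary point concerns grouping. Read literally, a placebo subject whose repeat came at Week 16 is Exposed in a table covering 12 weeks spent on placebo alone.

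**Working it through.** The documents state no figure on this point, so there is none to reproduce. The check follows the rules through dates and then asks how often each rule would be wrong.

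**Worked dates (PBO/SP-102 subject, AE ongoing)**

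- Index 14 Jan 2019, repeat 11 Mar 2019, start recorded as March 2019: imputed to 1 March and counted under Placebo. Recorded as 2019 only: imputed to 14 January.
- Index 12 Nov 2018, repeat 21 Jan 2019, start recorded as 2019 only: imputed to 1 January, before the repeat.

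Enumerating every index date in 2019, repeats on D29 to D141 and onsets on D1 to D169, every incomplete date that could fall on either side of the repeat was placed before it. Month-only starts in a month after the repeat are dated correctly.

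**Month-only starts in the repeat month: which rule errs less**

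Assume a 30-day month, repeat on day d = 2 to 30, onset day o uniform on 1 to 30, and duration L. Keep AEs with o >= d or o + L >= d. The post-repeat cells number 29 + 28 + ... + 1 = 435. The present rule is wrong for these cells, and imputing the repeat date is wrong for the pre-repeat cells.

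| Duration | Pre-repeat cells | Present rule wrong | Repeat date wrong |
|---|---|---|---|
| 3 days | 84 | 435/519 = 83.8% | 16.2% |
| 7 days | 182 | 435/617 = 70.5% | 29.5% |
| 14 days | 315 | 435/750 = 58.0% | 42.0% |
| ongoing | 435 | 435/870 = 50.0% | 50.0% |

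**Share of true post-repeat, month-only AEs that are misplaced**

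This depends on how soon they start. With onset within 7, 14 or 28 days of the repeat, every calendar day of 2017-2021 taken as the repeat day gives 86.9%, 75.4% and 52.4%. With onset uniform to D169 it is about 17% (repeats D29 to D141) or about 10% (repeat at D29).

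**Fully missing starts**

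Take onset uniform on D1 to D169. If the AE is ongoing, imputing the repeat date would be wrong for (repeat day - 1)/169: 28/169 = 16.6% at D29, 56/169 = 33.1% at D57, 84/169 = 49.7% at D85 and 140/169 = 82.8% at D141. Beyond about D85 it does worse than the present rule.

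**How many AEs**

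Assumptions, none from the documents: 60 to 140 PBO/SP-102 subjects (30-70% of 200), 0.5 post-repeat AEs each, 1-5% incomplete starts. This gives 60 x 0.5 x 0.01 = 0.3 to 140 x 0.5 x 0.05 = 3.5 AEs as an upper bound. If all were month-only with onset uniform to D169, about 17% of these, 0.05 to 0.6, would be misplaced. Moving one event of a rare term, with 100 subjects assumed, turns 1/100 (exact 95% CI 0.03-5.45%) into 0/100 (0-3.62%).

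**Exposed without a time limit**

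Assume 200 per arm, 30% of placebo subjects repeating at Week 8, a further 5%, 10% or 20% after Week 12, and AE rates of 2 per week on SP-102 and 1 on placebo (arbitrary units, true ratio 2.0). Misclassified subjects: 10/270 = 3.7%, 20/280 = 7.1%, 40/300 = 13.3% of Exposed. Events per subject relative to Not Exposed are (200x24 + 60x16 + late x 12)/n/12 = 1.81, 1.79, 1.73. With the limit: 5760/260/12 = 1.85.

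**The case against.** The strongest reply is that little depends on this.

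- The protocol's AE comparison is between four groups fixed by the injections received (Protocol 5.2.9). Moving an onset date changes nobody's group, and in SP-102/SP-102 subjects only the period changes. This stands.
- Listings show dates as recorded (SAP 7.3.4), all AEs are listed, and serious TEAEs and deaths have their own listings. An event lost from one table remains visible. This stands.
- Incomplete starts should be rare. The AE eCRF records start and end dates (Protocol 4), omissions are queried (Protocol 5.1), and repeat subjects have a call at 2 days and a visit at 14 days. This stands too.
- The override in SAP 7.3.4 may rescue cases. The safety evaluation and neurological examination at the repeat, or separately dated changes in intensity, can contradict an imputed earlier start. This stands in part: the override needs contradicting data, and a repeat date alone does not contradict an earlier onset.
- Any replacement rule errs as well. For ongoing month-only AEs, imputing the repeat date is no better (50% each). For fully missing starts it can be worse. This stands, and it limits the fix.
- On Exposed, the subject-level grouping is disclosed (SAP 7.4), and the Week 12 cutoff in SAP 7.1 may remove late repeats from the primary report; text beside it is redacted. But the cutoff is stated for the primary analysis, does not name the exposure grouping, and the outputs are rerun.

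A reader might infer that the trial's safety comparison is biased, or that repeat-injection AEs would be hidden. The first two replies show that the documents do not support either.

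**Conclusion.** The rule is mis-specified for the tables that use it. Month-only starts in the repeat month are put before the repeat, and year-only and fully missing starts tend the same way, always favouring SP-102 in PBO/SP-102 subjects. The reach is confined to the by-treatment, by-period and PBO/SP-102 within-subject AE tables.

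The number of affected AEs is unknown and probably very small; 0.3 to 3.5 is an assumed ceiling, not an estimate. The error shares rest on uniform onset. The 52-87% figures apply only to AEs starting within 28 days of the repeat and should not be read as the share of all incompletely dated AEs.

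It is tempting to conclude that every incomplete start should go to the repeat date. The arithmetic supports that only for the repeat month, where the change is never worse than the present rule under the model.

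The secondary point holds on a literal reading of the rerun. Under the stated assumptions it moves the ratio by 0.03 to 0.11. The limit does not restore the assumed 2.0, because subject-level grouping itself dilutes the contrast.

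This is a low-cost correction to consider before database lock.

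**What to change.** In SAP 7.3.5 add, for AEs: if a month-and-year start falls in the month of the repeat injection, and the AE is ongoing or stopped on or after the repeat, impute the repeat date unless other eCRF data contradict it. For PBO/SP-102 subjects this takes precedence when index and repeat share a month; for SP-102/SP-102 subjects the index-month rule stays. Leave the year-only and fully missing rules unchanged. Report how many AEs in repeat subjects had an imputed start, by type of missingness, so that the reader can judge whether any of this mattered.

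In the tables through 12 weeks (SAP 7.9 and 7.13.1), count a subject as Exposed only if SP-102 was received on or before the Week 12 cutoff of SAP 7.1. Keep the subject-level grouping.

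The cost is a few lines of text and programming, using dates already collected. There are four downsides:

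- Some true pre-repeat AEs move to the post-repeat period (the 16-50% above).
- First-injection counts in SP-102/SP-102 subjects fall slightly, which is not conservative for single-injection safety.
- The shared-month clause treats the arms differently and is a conservative choice rather than a more accurate date. A repeat at least 28 days after the index can share its month only when the index is on the 1st, 2nd or 3rd; for a repeat on D29 that is 29 of 365 index dates.
- An AE imputed to a repeat date after the Week 12 cutoff drops out of the 12-week tables.

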### **7.3.6 Inexact Values**

In the case where a laboratory parameter has result recorded as “> x”, “≥ x”, “< x” or “≤ x”, a value of x will be used for analysis purposes.

### **7.3.7 Electrocardiogram Data**

If more than one value is recorded at a time point for electrocardiogram (ECG) data recorded on a continuous scale, the integer of the mean value will be recorded. For overall interpretation if more than one value is recorded, the most severe (worst case) of the respective readings will be taken.

### **7.3.8 Unscheduled Visits**

Only scheduled post-baseline laboratory and vital signs values will be tabulated. Post-baseline repeat/unscheduled (except for repeat injection visits) assessments will be disregarded, although these post-baseline assessments will be listed in the relevant appendices to the CSR.

Repeat injection visits maybe captured as unscheduled visits. All assessments carried out during a repeat injection visit will be included in the analysis.

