[REDACTED] Eligible subjects will then be randomly assigned (in a 1:1 ratio) on D1 to receive a single dose of an SP-102 TF, or placebo [REDACTED] in the vicinity of the epidural space or [REDACTED] under fluoroscopic guidance (for instructions on study drug injection see [Appendix D](#)). This first injection is referred to as the “index injection”. An appropriately trained physician, hereafter called the Injection Physician, administering the DB investigational product (IP) and other assisting staff (eg, nurse) will, therefore, not be blinded to the treatment assignment, while the rest of study staff involved in assessments and collection of data will remain blinded. Procedures will be in place at each site to ensure blinding, minimizing personnel involved with injection, and guarantee sequestration of imaging data acquired at the time of injection.

Fluoroscopic imaging guidance is required by this protocol to ensure proper placement of the injection needle (see instructions in [Appendix D](#)). Long-term persistent AEs are rarely seen with fluoroscopically-guided lumbosacral TF injections, however immediate and delayed AEs may include vasovagal episodes, procedure interruption from intravascular flow, pain exacerbation, injection site soreness, headache, and insomnia ([Plastaras-2015](#)). Avoidance of risk of procedural AEs in the placebo group by implementing an [REDACTED]

[REDACTED] is consistent with ethical considerations and use of [REDACTED] in interventional/surgical clinical trials (Wartolowska-2014). In addition to safety considerations and lowering the risk of procedural complication in the control group, the choice of an [REDACTED]

The choice of the TF injection approach with direct deposition of drug near the ventral epidural space at the affected level is selected based on published reviews documenting better effectiveness as compared to other approaches. For lumbar disc herniation with unilateral symptoms, the evidence for analgesic effect and ability to prevent surgery is greater for TF epidural injections as compared to caudal or interlaminar approaches (Manchikanti-2012; Cohen-2013).

[figure not shown]

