3.5.7 Safety Assessments

3.5.7.1 Physical Examination:

A complete physical examination, including examination of general appearance, skin, neck, eyes, ears, nose, throat, heart, lungs, abdomen, lymph nodes, extremities, and musculoskeletal system, will be performed at Screening. Specific musculoskeletal examination focusing on lumbar spine and lower extremities to exclude musculoskeletal sources of the predominant pain, such as SI joints and trigger points, will be performed in standardized manner and recorded. Height (in inches without shoes) and weight (in pounds) will be recorded at Screening.

3.5.7.2 General Neurological and Targeted Neurological Examinations:

A general neurological examination will include evaluation of mental status (awareness of person, place, and time), cranial nerves, motor function and balance, sensory exam (ability to feel) and reflexes. A targeted neurological examination demonstrating findings of, focusing on signs and symptoms of lumbosacral radiculopathy, including straight leg raise test, will be performed according to the checklist (see [Appendix A](#)). Both general and targeted neurological exams are to be performed by the same trained clinician throughout the study, if possible. Training for conducting examination will be available on video. General and targeted neurological examinations will be performed at Screening, Baseline (D1), W2, W4, W12, and W24, as well as if the repeat injection is administered.

The blinded Investigator will summarize and document the MRI findings based on the Lumbar Disc Nomenclature, the clinical presentation, and the Injection Plan in the eCRF prior to Baseline (D1).

3.5.7.3 Vital Signs and Body Weight:

Vital signs will include systolic and diastolic BP and heart rate. During the usual clinic visits, the subject is to be seated for approximately 3 mins before vital signs are recorded. During the injection procedure, the vital signs will need to be collected while the subject is in prone position on the fluoroscopy table ([Appendix D](#)). Vital signs will be recorded at each clinic visit.

3.5.7.4 Electrocardiogram:

Standard 12-lead ECGs will be measured on the site machines at Screening. The ECG results will be documented in the eCRF.

3.5.7.5 Laboratory Parameters:

The following clinical laboratory tests are to be performed at Screening and W24 unless noted below:

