Hematology: Hemoglobin, hematocrit, red blood cell count, WBC count (with differential [lymphocytes, neutrophils, eosinophils, basophils, and monocytes]), and platelet count.

Blood Chemistry: albumin, alkaline phosphatase, AST, ALT, direct bilirubin, total bilirubin, blood urea nitrogen, calcium, chloride, creatine kinase (Screening only), creatinine, gamma-glutamyl transferase, glucose, lactate dehydrogenase, potassium, sodium, and uric acid.

Other tests: HbA1c, HIV, hepatitis B, and hepatitis C at Screening. Coagulation tests at Screening: activated PTT, PT, and INR. Coagulation tests may be repeated prior to the index and repeat injection, if deemed necessary by the Investigator.

Urinalysis: Dipstick analysis: color, turbidity, specific gravity, pH, glucose, protein, ketones, urobilinogen, bilirubin, blood nitrate, leukocyte esterase, and microscopic examination when indicated by dipstick results.

Urine drug screen: Includes opiates, barbiturates, benzodiazepines, tricyclic antidepressants, cannabinoids, PCP, cocaine, ecstasy, and amphetamines. A urine drug screen will be obtained at Screening, Baseline (D1), W2, and W4. A urine drug screen may be repeated if deemed necessary by the Investigator.

For females of childbearing potential: Serum pregnancy test at Screening. Urine pregnancy test at Baseline (D1) and at Repeat Injection. A urine pregnancy test may be repeated if deemed necessary by the Investigator.

Laboratory samples will be analyzed by a central laboratory [REDACTED] to ensure consistent interpretation of results. Samples are to be shipped to [REDACTED], [REDACTED]. In the event of an unexplained clinically noteworthy abnormal laboratory test value, the test should be repeated immediately and followed up until it has returned to the normal range and/or an adequate explanation of the abnormality is found.

3.5.7.6 Adverse Events:

All AEs occurring after the subject signs the ICF through W24, D169 will be recorded. See [Section 4](#) for additional information.

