#### 7.3.2 Baseline

Except otherwise specified, baseline is defined as the last non-missing value (either scheduled, unscheduled or repeat) before the subject receives the first dose of SP-102 TF or placebo injection on D1. Baseline calculations for variables collected in the diary are described in the efficacy analyses section.

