### 7.13.2 Laboratory Data

Descriptive statistics of the observed values and change from baseline (continuous data) will be presented by treatment group and visit for each hematology (hemoglobin, hematocrit, red blood cell count, white blood cell (WBC) count (with differential [lymphocytes, neutrophils, eosinophils, basophils, and monocytes]), platelet count, hemoglobin A1c, activated partial thromboplastin time, prothrombin time and international normalization ratio), urinalysis (color, turbidity, specific gravity, pH, glucose, protein, ketones, urobilinogen, bilirubin, blood nitrate, leukocyte esterase, and microscopic examination) and serum chemistry (albumin, alanine aminotransferase [ALT], alkaline phosphatase, aspartate aminotransferase [AST], direct bilirubin, total bilirubin, blood urea nitrogen, calcium, chloride, creatine kinase, creatinine, gamma-glutamyl transferase, glucose, lactate dehydrogenase, potassium, sodium, uric acid) parameter. Each measurement (continuous data) will be classed as below, within, or above normal range, based on ranges supplied by the laboratory used. Laboratory data will be summarized for the secondary analysis period.

Shift tables in relation to the normal range from baseline to each follow-up visit will be presented.

All other laboratory tests will be listed only. This includes troponin I, troponin T, lipid panel, plasma cortisol, human immunodeficiency virus (HIV), hepatitis B, hepatitis C, and serum

pregnancy test (females of childbearing potential only), cortisol, urine drug screen, and urine pregnancy test.

A listing of abnormal laboratory measurements defined as any out of normal range laboratory values recorded throughout the study will be presented.

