### 7.13.3 Vital Signs

Descriptive statistics for observed values and changes from baseline in the following vital signs will be presented by treatment group, visit, and timepoint within visit:

- Systolic blood pressure (mmHg)
- Diastolic blood pressure (mmHg)
- Pulse rate (Heart Rate) [bpm]

Vital signs data will be summarized separately for both the primary and the secondary analysis periods. Vital sign values will be categorized into the following potential clinical concern categories if applicable, and then summarized.

[figure not shown]
Vital Sign	Potential Clinical Concern Categories
Systolic blood pressure	$\geq 160$ mmHg
Diastolic blood pressure	$\geq 100$ mmHg
Pulse rate (Heart Rate)	$< 60$ or $> 100$ bpm

All vital sign measurements including the position of the subject when the measurement was taken will be listed.

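### Outside repeat-injection and early-termination visits, unscheduled post-injection laboratory and vital-sign readings are listed but left out of the shift and clinical-concern tables

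*SAP*

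**What the plan says.** SAP 7.3.8 sets the rule for both data types: "Only scheduled post-baseline laboratory and vital signs values will be tabulated". It then adds: "Post-baseline repeat/unscheduled (except for repeat injection visits) assessments will be disregarded". The values set aside go to appendix listings. Repeat-injection visits may themselves be captured as unscheduled, and everything assessed at them enters the analysis. SAP 7.3.9 assigns early-termination laboratory and vital-sign readings to Week 24.

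Protocol 3.5.7.5 fixes the laboratory timing: "The following clinical laboratory tests are to be performed at Screening and W24 unless noted below". Protocol 3.5.7.3 has vital signs taken at each clinic visit.

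The outputs affected are in SAP 7.13.2, "Shift tables in relation to the normal range from baseline to each follow-up visit will be presented", and SAP 7.13.3, "Vital sign values will be categorized into the following potential clinical concern categories if applicable, and then summarized". The visible text of these two sections describes no worst-value or any-time row. SAP 7.13.2 does promise a listing of all out-of-range laboratory values from the whole study. Protocol 5.2.9.3 asks that every laboratory reading be placed below, inside or above the normal range, and SAP 7.13.2 says much the same of every continuous measurement.

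**The concern.** Changes from baseline in laboratory parameters and in vital signs are named safety endpoints in Protocol 5.2.9 and SAP 4.4. A shift table is where a reader looks for how many subjects in each group moved outside the normal range. If a reading is taken between planned visits because a subject is unwell, and the finding settles before the next planned visit, the table has no cell for it. The listing holds the value but gives no count by group. A study report could then show few or no shifts while its own appendix contains several. The exposure is greatest for laboratory tests, where planned post-injection sampling is sparse.

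**Working it through.** The plan states no figure to reproduce, and the documents do not give the number of unscheduled readings. The check is therefore a count of time points, followed by a reading of the rules against each other.

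**1. Scheduled time points after the index injection**

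- Routine haematology and chemistry (Protocol 3.5.7.5): Screening and W24, so 2 − 1 = 1 post-injection draw. W24 is D169, and 169 − 1 = 168 days = 24 weeks after the injection. The listed exceptions do not add a routine draw: urine drug screens at W2 and W4, a urine pregnancy test at repeat injection, and optional coagulation tests before an injection.
- Vital signs (Protocol 3.1 and 3.5.7.3): D15, D29, D57, D85, D113, D141 and D169, which is 7 clinic visits. The first comes 15 − 1 = 14 days after the injection. From D29 the visits are 28 days apart (for example 57 − 29 = 28).

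**2. Where a post-injection laboratory value ends up**

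| Situation | Shift table | Listing | AE tables |
|---|---|---|---|
| Abnormal at an unscheduled visit, resolved by W24 | No; shows as normal-to-normal if baseline was normal | Yes | Only if a Protocol 4.1.4 criterion is met |
| Abnormal at an unscheduled visit, still abnormal at W24 | Yes, through W24 | Yes | Only if a criterion is met |
| Abnormal at scheduled W24, then retested | Yes; the W24 value stays | Yes, both | Only if a criterion is met |
| Taken at a repeat-injection visit | Included in the analysis (7.3.8) | Yes | Only if a criterion is met |
| Taken at early termination | Yes, mapped to W24 (7.3.9) | Yes | Only if a criterion is met |

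The first row is the gap. As a hypothetical case, take a subject with normal glucose at baseline, a raised value at an unscheduled Day 5 visit, and a normal value at W24. The shift table records normal-to-normal.

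**3. Direction.** The number of subjects abnormal at any time after injection cannot be smaller than the number abnormal at W24, among subjects with a W24 value. The scheduled-only table can therefore match or understate the any-time count in a group, but not exceed it. The documents do not show which arm would be affected more.

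**4. The first report.** SAP 7.1 plans a report with safety data up to Week 12 (D85). The single routine draw falls 169 − 85 = 84 days later. On the visible text, the only routine post-injection laboratory values able to enter that report's tables come from repeat-injection or early-termination visits.

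**5. Attribution.** Subjects in either arm may receive open-label SP-102 between W4 and W20. For them the W24 draw follows both injections and cannot separate the two.

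**6. Consistency with the protocol.** Classifying every reading (Protocol 5.2.9.3) and setting unscheduled ones aside (SAP 7.3.8) do not agree. The visible entries in SAP section 11, part of which is redacted, do not declare the change.

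**The case against.** The strongest reply is that scheduled-only by-visit tables are a conventional presentation, and that nothing is concealed. The values are listed. Every out-of-range laboratory result has its own listing. Protocol 4.1.4 makes an abnormality an AE when it needs treatment or further tests, leads to discontinuation of investigational product, comes with symptoms, or is judged clinically significant. A marked abnormality found because of a symptom would often qualify and be counted by organ class, term and intensity. This stands, and it limits the harm. It does not remove it: AE entry depends on those criteria, and a listing compares nothing between groups.

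Four stronger readings are tempting, and the documents do not support them.

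- *Every interim value is lost from the safety tables.* Repeat-injection visits are exempt, early-termination readings go to Week 24, and AE tables remain a route. No percentage can be put on the loss, because the number of draws is unknown.
- *Dropped readings are always the abnormal ones.* The protocol's retest instruction says "the test should be repeated immediately and followed up until it has returned to the normal range". After an abnormal scheduled value, such retests drift toward normal, and leaving them out protects the abnormal result. The concern applies to readings that begin at an unscheduled visit.
- *The rule is unfair because baseline may use unscheduled values.* SAP 7.3.2 says "baseline is defined as the last non-missing value (either scheduled, unscheduled or repeat) before the subject receives the first dose". That is an ordinary pre-dose definition and serves a different purpose from allocating later values to visits.
- *Low blood pressure cannot be flagged, so vasovagal or adrenal events are missed.* The categories are the protocol's own (5.2.9.4) and include heart rate below 60. Protocol 3.1 treats these episodes as AEs ("immediate and delayed AEs may include vasovagal episodes"). The link from adrenal suppression to low blood pressure is not in the documents. None of this concerns SAP 7.3.8.

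**Conclusion.** The point holds in a limited form. Unscheduled post-injection laboratory and vital-sign readings, other than those from repeat-injection or early-termination visits, cannot reach the shift or clinical-concern tables as described. For routine haematology and chemistry, one visible planned draw at 168 days means that a transient abnormality can leave no trace in any summary table unless it is reported as an AE. For vital signs the gap is smaller, with seven planned visits.

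The size in subjects is unknown. The primary and key secondary inferences are untouched, so this is a low-cost improvement to safety reporting and not a flaw in the trial's main conclusion.

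The conclusion rests on visible text. The schedule of assessments and the SAP's table list are redacted, so additional planned draws or an existing any-time table cannot be ruled out. The SAP also does not say whether the clinic visit 14 days after a repeat injection counts as scheduled for this rule.

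**What to change.** First confirm, from the unredacted table list, that no worst-value or any-time table is already planned. If none is:

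1. Leave by-visit means and changes on scheduled values, as SAP 7.3.8 has them.
2. Add to SAP 7.13.2 a shift table from baseline to the worst post-injection value, using scheduled and unscheduled readings. Define worst separately in the low and high directions for each test.
3. Add to SAP 7.13.3 the number of subjects with any post-injection reading in each existing clinical-concern category, from all readings.
4. Split both at the repeat injection, so that values after open-label SP-102 are not credited to the index treatment.
5. State in SAP 7.3.8 how the 14-day visit after a repeat injection is classed. Record in SAP section 11 that by-visit tables use scheduled values only.

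The cost is SAP wording and a few table rows; the values are already collected and listed. Two cautions belong in a footnote: abnormal counts may rise, and for-cause readings are not evenly timed across subjects, so the number of subjects with any unscheduled reading should be shown by group beside the counts.
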